7.2. Study Drug Administration

The investigator or designee is responsible for:

- explaining the correct use of the investigational agents and planned duration of each individual's treatment to the site personnel and patient/legal representative,
- verifying that instructions are followed properly,

- maintaining accurate records of study drug dispensation, destruction, and collection, and returning or destroying all unused medication to Lilly or its designee at the end of the study.

Patients will be instructed to contact the investigator as soon as possible if they have a complaint or problem with the study drug(s) so that the situation can be assessed.

7.2.1. Dosing Schedule

This study defines 1 cycle as 4 weeks or 28 days.

LY2510924 will be self-administered prior to the start of durvalumab infusion on the days both drugs are given together.

7.2.1.1. LY2510924

In Phase 1a, LY2510924 will be self-administered SQ at rotated injection sites every day for 28 days as outlined in a dose escalation schema; in Phase 1b, LY2510924 will be self-administered SQ for 28 days at the selected Phase 1a dose.

Approximately 30 minutes prior to dose administration, the vials should be removed from the refrigerated storage area 2°C to 8°C and allowed to equilibrate to ambient room temperature prior to injection. Study drug must be administered within 6 hours after removal from the refrigerated storage area.

Doses that are missed should not be made up.

On Day 1 of Cycles 1 to 4 and Cycle 6, LY2510924 should be self-administered at the clinic (time and date recorded) **after a blood sample is taken for LY2510924 PK but prior to the start of durvalumab**. Additionally, on Cycle 1 Days 2, 15, and 16, LY2510924 should be self-administered at the clinic (time and date recorded) **after a blood sample is taken for LY2510924 PK**.

7.2.1.2. Durvalumab

Each patient will receive IV administration of durvalumab 1500 mg on Day 1 of each cycle. This administration will be given at least 30 minutes after LY2510924.

Preparation of durvalumab doses for administration with an IV bag

The preparation of infusion bags should be done under aseptic conditions by trained personnel.

A dose of 1500 mg durvalumab will be administered using an IV bag containing 0.9% (w/v) saline or 5% (w/v) dextrose, with a final durvalumab concentration ranging from 1 to 20 mg/mL, and delivered through an IV administration set with a 0.2- or 0.22- μ m in-line filter. Remove 30.0 mL of IV solution from the IV bag prior to addition of durvalumab. Next, 30.0 mL of durvalumab (ie, 1500 mg of durvalumab) is added to the IV bag such that final concentration is within 1 to 20 mg/mL (IV bag volumes 100 to 1000 mL). Mix the bag by gently inverting to ensure homogeneity of the dose in the bag.

Prior to the start of the infusion, ensure that the bag contents are at room temperature to avoid an infusion reaction due to the administration of the solution at low temperatures.

Vials should be used for specific patients and should not be shared between patients.

Dose administration

Durvalumab will be administered at room temperature (approximately 25°C) by controlled infusion via an infusion pump into a peripheral or central vein.

Following preparation of durvalumab, the entire contents of the IV bag should be administered as an IV infusion over approximately 60 minutes (± 5 minutes), using a 0.2, or 0.22- μm in-line filter.

The IV line should be flushed with a volume of IV solution (0.9% [w/v] saline or 5% [w/v] dextrose) equal to the priming volume of the infusion set used after the contents of the IV bag are fully administered, or complete the infusion according to institutional policy to ensure the full dose is administered and document if the line was not flushed.

Since the compatibility of durvalumab with other IV medications and solutions, other than 0.9% (w/v) saline or 5% (w/v) dextrose, is not known, the durvalumab solution should not be infused through an IV line in which other solutions or medications are being administered.

Standard infusion time is approximately 1 hour. However, if there are interruptions during infusion, the total allowed time should not exceed 8 hours at room temperature as shown in [Table CXAD.7.1](#).

Table CXAD.7.1. Durvalumab Hold and Infusion Times

Maximum time from needle puncture to start of administration	4 hours at room temperature, 24 hours at 2°C to 8°C
Maximum time for IV bag infusion, including interruptions	8 hours at room temperature

Abbreviation: IV = intravenous.

In the event that either preparation time or infusion time exceeds the time limits outlined in [Table CXAD.7.1](#), a new dose must be prepared from new vials. Durvalumab does not contain preservatives, and any unused portion must be discarded.

No incompatibilities between durvalumab and polyvinylchloride or polyolefin IV bags have been observed.

Monitoring of dose administration

Patients will be monitored during and after the infusion with assessment of vital signs.

On durvalumab treatment days, measure blood pressure, pulse, temperature, and respiratory rate prior to the first infusion of the day, and as clinically indicated.

- Measure blood pressure, pulse, temperature, and respiratory rate after the LY2510924 injection (but prior to the durvalumab infusion), and as clinically indicated.
- Measure blood pressure, temperature, and pulse at the following time points (based on a standard 60 (±5)-minute infusion):
 - before the start of infusion (up to 30 minutes prior)
 - during the infusion at 30 (±5) minute intervals, including when the infusion might be prolonged due to an interruption
 - at the end of infusion at 60 (±5) minutes
 - during the 1-hour post-infusion observation period, 30 (±5) and 60 (±5) minutes after the end of infusion

If the infusion takes longer than 60 minutes, then blood pressure, temperature, and pulse measurements should follow the principles described here or more frequently if clinically indicated.

A 1-hour observation period is required after all durvalumab infusions. If the patient shows no evidence of an infusion-related reaction (IRR) with the first 2 infusions of each study drug, then for subsequent infusions, no observation period is required after each subsequent infusion. In the event an IRR occurs thereafter, the 1-hour observation between infusions should be reinstated.

In the event of a \leq Grade 2 IRR, the infusion rate of study drug may be decreased by 50% or interrupted until resolution of the event (up to 4 hours) and re-initiated at 50% of the initial rate until completion of the infusion. For patients with a \leq Grade 2 IRR, subsequent infusions may be administered at 50% of the initial rate. Acetaminophen and/or an antihistamine (eg, diphenhydramine) or equivalent medications per institutional standard may be administered at the discretion of the investigator. If the IRR is \geq Grade 3 or higher in severity, both study drugs will be discontinued.

In the event of an IRR, blood samples will be collected for both PK (durvalumab and LY2510924) and immunogenicity (durvalumab) analysis at the following time points: (i) as close as possible to the onset of the IRR, (ii) at the resolution of the IRR, and (iii) 30 days following the IRR.

As with any antibody, allergic reactions to dose administration are possible. Appropriate drugs and medical equipment to treat acute anaphylactic reactions must be immediately available, and study personnel must be trained to recognize and treat anaphylaxis. The study site must have immediate access to emergency resuscitation teams and equipment in addition to the ability to admit patients to an intensive care unit if necessary.

7.2.2. Phase 1a Dose Escalation

The MTD of LY2510924 determined during Phase 1a will be used for Phase 1b.

Three dose levels will be investigated in Phase 1a ([Figure CXAD.6.1](#)). Dose escalation is described in Section [7.2.2.2](#).

Because Phase 1a is the dose-escalation part of the study, data will be evaluated on an ongoing basis until the MTD is determined. Safety data, in particular AEs, will be the primary criteria for the dose escalation. No dose escalation can occur without prior discussion and agreement between the investigator and the Lilly study team in consultation with the collaborator.

No inpatient dose escalation or reduction is allowed during Phase 1a.

Dose escalation will be based on the number of DLTs experienced during Cycle 1.

7.2.2.1. Dose-Limiting Toxicity Determination and Maximum-Tolerated Dose Definition

A DLT is defined as 1 of the following AEs reported during the Phase 1a DLT observation period, if considered to be definitely, probably, or possibly related to either study regimen by the investigator; and fulfills any 1 of the following criterion using National Cancer Institute (NCI) CTCAE version (v) 4.03:

1. Non-laboratory abnormalities (clinical toxicity):
 - a. Any Grade 4 immune-related AE ([Attachment 10](#))
 - b. Any Grade 4 non-laboratory AE
 - c. Any CTCAE Grade ≥ 3 QT prolongation AE
 - d. Any \geq Grade 3 colitis or noninfectious pneumonitis irrespective of duration
 - e. Any Grade 3 immune-related AE (excluding colitis, QT prolongation, or pneumonitis) ([Attachment 10](#)) that does not downgrade to Grade 2 within 3 days after onset of the event despite optimal medical management including systemic corticosteroids, or does not downgrade to \leq Grade 1 or baseline within 14 days
 - f. Any Grade 2 pneumonitis that does not resolve to \leq Grade 1 within 3 days of the initiation of maximal supportive care, including corticosteroid therapy
 - g. Grade 3 toxicity lasting an extended period of time despite optimal supportive care (for example, nausea, vomiting, and diarrhea lasting >3 days; fatigue lasting >7 days)
2. Laboratory abnormalities:
 - a. Any Grade 3 laboratory value if:
 - i. Medical intervention is required to treat the patient, or
 - ii. Associated with clinically significant symptoms. Examples include but are not limited to, \geq Grade 3 thrombocytopenia if associated with bleeding and requires platelet transfusion, \geq Grade 3 febrile neutropenia, or
 - iii. The abnormality persists for >7 days (excluding amylase and lipase)
 - b. Any Grade 4 laboratory abnormalities
 - c. Liver transaminase elevation $>8 \times$ upper limit of normal (ULN) or total bilirubin $>5 \times$ ULN

Note: Liver test abnormality: For HCC patients and patients with liver metastasis who begin treatment with Grade 2 AST or ALT, if AST or ALT increases by 2-fold greater than baseline and lasts for >7 days

- d. ANC >75,000/ μ L or \geq Grade 3 leukocytosis (leukocytes >100,000/ μ L) of any duration, or leukocytosis/granulocytosis causing clinical symptoms
3. Grade 5 toxicity (that is, death)
4. Any other significant toxicity deemed by the primary investigator and Lilly clinical research personnel to be dose limiting, for example:
 - a. Any toxicity that is possibly related to study treatment that requires the withdrawal of the patient from the study during Cycle 1 (including Day 15), or
 - b. A delay of >14 days in initiating Cycle 2 due to persistent Grade >2 toxicities
5. Any other \geq Grade 3 toxicity, except for the exclusions listed below.

The definition excludes the following conditions:

- Toxicity that is clearly and directly related to the primary disease or to another etiology is excluded from this definition
- Grade 3 endocrine disorder (thyroid, pituitary, and/or adrenal insufficiency) that is managed with or without systemic corticosteroid therapy and/or hormone replacement therapy and the patient is asymptomatic
- Grade 3 inflammatory reaction attributed to a local antitumor response (for example, inflammatory reaction at sites of metastatic disease, lymph nodes, etc.)
- Concurrent vitiligo or alopecia of any AE grade
- Grade 3 IRR (first occurrence and in the absence of steroid prophylaxis) that resolves within 6 hours with appropriate clinical management
- Grade 3 or 4 neutropenia that is not associated with fever or systemic infection that improves by at least 1 grade within 3 days. Note: Grade 3 or Grade 4 **febrile** neutropenia will be a DLT regardless of duration or reversibility.
- Grade 3 or 4 lymphopenia
- Grade 3 thrombocytopenia that is not associated with bleeding that requires clinically significant medical intervention and improves by at least 1 grade within 3 days
- Isolated Grade 3 electrolyte abnormalities that are not associated with clinical signs or symptoms and are reversed with appropriate maximal medical intervention within 3 days

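### DLT criterion 5 counts every other related Grade 3 or higher toxicity, which cancels the conditions in criteria 1.e, 1.g and 2.a or is itself nearly empty; the text does not say which

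*Protocol*

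**What the plan says.** The lead-in to Protocol Section 7.2.2.1 sets two requirements. The event must be "definitely, probably, or possibly related to either study regimen by the investigator", and it must be one that "fulfills any 1 of the following criterion". The criteria are therefore alternatives, and one is enough.

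For Grade 3 events several criteria carry conditions:

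- **1.e** (immune-related) counts an event "that does not downgrade to Grade 2 within 3 days after onset of the event" under optimal management, or that is not back to Grade 1 or baseline within 14 days.
- **1.g** (clinical toxicity) requires prolonged duration despite supportive care, with the examples "nausea, vomiting, and diarrhea lasting >3 days; fatigue lasting >7 days".
- **2.a** (laboratory values) requires an intervention, or clinically significant symptoms, or persistence beyond 7 days. The persistence limb exempts amylase and lipase.
- **2.c** sets its own thresholds for transaminases (above 8 x ULN) and bilirubin (above 5 x ULN).

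Grade 4 events are covered without such conditions by 1.b ("Any Grade 4 non-laboratory AE") and 2.b ("Any Grade 4 laboratory abnormalities"), and Grade 5 by criterion 3. Criterion 4 lets the primary investigator and the sponsor jointly declare other toxicities dose limiting.

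Criterion 5 then adds any other event at or above "Grade 3 toxicity, except for the exclusions listed below". Nine exclusions follow. SAP Section 6.8.2 summarizes DLTs but does not define them.

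**The concern.** Criterion 5 carries none of the conditions that 1.e, 1.g and 2.a impose, and everything turns on the word *other*. If it means any Grade 3 event that did not already qualify, the earlier conditions have no effect outside the exclusion list. If it means a kind of toxicity not addressed above, criterion 5 has almost no content.

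Identifying DLTs and the MTD is the Phase 1a primary objective (Section 5.4.1). Section 7.2.2 bases escalation on the number of DLTs in Cycle 1, and the Attachment 9 model is fitted to that count. DLT status also decides whether a patient who stops before completing Cycle 1 is evaluable (Section 7.2.2.2). The DLT-equivalent definition in Section 7.2.4, and through it the one-third review trigger for Phase 1b in Section 10.10, reuse the same criteria. Two assessors following the text could supply different counts from the same patients.

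**Working it through.** **Step 1: apply both readings to the same events.** All events are assumed related. *Literal* means criterion 5 catches any Grade 3 event not already counted. *Narrow* means it catches only kinds of toxicity not addressed in 1 to 4.

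| Event | Specific criterion | Exclusion applies? | Literal | Narrow |
|---|---|---|---|---|
| Grade 3 fatigue, 5 days | 1.g example (over 7 days) not met | No | DLT | Not automatic |
| Grade 3 lipase, 10 days, no symptoms or treatment | Exempt under 2.a.iii | No | DLT | Not automatic |
| Grade 3 platelets, no symptoms or treatment, not improved by day 3, recovered within 7 days | 2.a not met | No, 3-day limit missed | DLT | Not automatic |
| Grade 3 immune-related rash, Grade 2 by day 2, Grade 1 by day 10 | 1.e not met | No | DLT | Not automatic |

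Under the narrow reading criterion 4 could still make any of these a DLT by joint judgement. Criterion 4 adds DLTs and removes none.

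The overlap extends to 2.c. The hepatitis table in Attachment 11 grades AST or ALT above 5 and up to 20 x ULN as Grade 3. A rise to 6 x ULN is below the 2.c threshold yet falls in criterion 5 on the literal reading.

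**Step 2: what the narrow reading leaves in criterion 5.** Grade 5 belongs to criterion 3 and Grade 4 to 1.b and 2.b. Grade 3 events are laboratory values (2.a), immune-related (1.d, 1.e) or other clinical toxicity (1.g). Almost nothing remains.

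**Step 3: the model, checked against the plan's own figures.** Attachment 9 gives logit p(d) = α + β·log(d/40). (α, log β) is bivariate normal with means (−1.09, 0.26), SDs (2.17, 0.51) and correlation −0.89. Numerical integration gives prior median DLT probabilities at 10/20/30/40 mg of 0.052/0.12/0.187/0.252, against 0.06/0.12/0.18/0.26 in Table App.1. Each agrees within 0.01.

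**Step 4: effect of one reclassified event.** The posterior is proportional to the prior times the product over doses of p(d)^x·(1−p(d))^(n−x), with x DLTs in n patients. Overdose means p(d) > 0.33, and a dose is dropped if its posterior overdose probability exceeds 0.25.

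| Data | 20 mg | 30 mg | 40 mg |
|---|---|---|---|
| 20 mg: 0/3 | 0.05 | 0.09 | 0.14 |
| 20 mg: 1/3 | 0.38 | 0.53 | 0.65 |
| 20 mg: 0/6 | 0.01 | 0.03 | 0.06 |
| 20 mg: 1/6 | 0.12 | 0.254 | 0.39 |
| 20 mg 0/3, 30 mg 0/3 | 0.01 | 0.02 | 0.05 |
| 20 mg 0/3, 30 mg 1/3 | 0.08 | 0.18 | 0.30 |
| 20 mg 0/3, 30 mg 1/6 | 0.02 | 0.06 | 0.14 |
| 20 mg 0/3, 30 mg 2/6 | 0.09 | 0.23 | 0.40 |
| 20 mg 0/3, 30 mg 0/3, 40 mg 1/3 | 0.01 | 0.04 | 0.10 |

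One event among the first three patients takes all three planned doses over the limit. Enlarging that cohort to 1/6 brings 20 mg back but leaves 30 mg marginally over. At 30 mg, one event moves 40 mg across the limit in both the 3-patient and 6-patient comparisons. After two clean cohorts, one event at 40 mg excludes nothing.

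**Step 5: Phase 1b trigger.** With 6 patients, one reclassified event moves 1/6 = 0.17 to 2/6 = 0.33, which meets the one-third threshold.

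**Step 6: frequency, by assumption only.** At the 20 mg prior median of 0.12, the chance of at least one DLT in 3 patients is 1 − 0.88³ = 0.319. If the literal reading added 5, 10 or 20 percentage points per patient (assumed, since the documents give no rate), it would be 1 − 0.83³ = 0.428, 1 − 0.78³ = 0.525 or 1 − 0.68³ = 0.686.

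**The case against.** The best defence is that the text already favours the literal reading. The criteria form a union, so failing 1.e, 1.g or 2.a removes nothing from criterion 5, and criterion 5 names its own limit, the exclusion list. The exclusions for a Grade 3 infusion reaction resolving within 6 hours and for thrombocytopenia improving within 3 days do little unless criterion 5 is broad. Attachment 13 shows amendment (b) deleting a restriction to non-hematological toxicity from it. The platelet example is weaker for the same reason: missing the 3-day limit suggests the event was meant to count. The fatigue duration in 1.g is only an example. This stands as evidence of a lean.

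It does not settle the point. Nothing defines *other*. The literal reading leaves three conditioned criteria without effect beyond the exclusions, and the amylase and lipase exemption pointless. The amendment (b) rationale in Section 5.3 presents the Grade 3 laboratory conditions as requirements. That evidence is limited, because it joins symptoms and persistence with *and* where the current 2.a uses *or*.

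The model figures show what any single DLT does under a diffuse prior, not how often this ambiguity would bite. Before any data the prior puts the overdose probability at 20 mg at 0.305, already above 0.25. That limitation is accepted.

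The safeguards are real. Attachment 9 lets the team depart from the model. Section 7.2.2.2 requires investigator and sponsor agreement in writing, and allows more patients after a DLT. Phase 1b toxicity is evaluated continuously, and the one-third threshold prompts only a review. These help a disagreement surface and limit its consequences, but none gives a rule for classifying the event.

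**Conclusion.** The concern holds. As written, Section 7.2.2.1 gives some related Grade 3 events two possible classifications and no sentence to choose between them. The problem is confined to Grade 3 events that miss the conditions in 1.e, 1.g, 2.a or 2.c and are not on the exclusion list; Grade 4 and Grade 5 events are not affected.

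The potential effect is one DLT more or less in a cohort of three to six. In the early cohorts that can decide whether a planned dose passes the 0.25 limit, and in others it changes nothing. The model results rest on the Attachment 9 prior and on decisions following the model. The number of events affected is unknown. The literal reading counts more DLTs and is cautious for patients; its cost is possible under-escalation. This should be fixed because it concerns the definition behind the Phase 1a primary objective. Which reading is clinically right is not judged here.

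**What to change.** Reconcile criterion 5 with the criteria before it. State in criterion 5 whether Grade 3 events addressed by 1.e, 1.g, 2.a and 2.c fall inside or outside it. Then align the time limits in the exclusion list and the amylase and lipase exemption with that statement, so that each event has one classification before any escalation decision. The choice of clinical rule belongs to the sponsor's clinicians.

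Sections 7.2.4 and 10.10 would follow automatically, since they rely on the same criteria. The cost is a wording amendment to Section 7.2.2.1, with no added patients or procedures.

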7.2.2.2. Dose-Escalation Method

Adaptive scheme, with incorporation of a Bayesian model-based, toxicity-band method (Neuenschwander et al. 2008), will be used to assess the safety of LY2510924 given in combination with durvalumab. The Bayesian model-based, toxicity-band method incorporates the prior expectations of the dose-toxicity curve and the observed DLT data after each cohort and provides quantitative guidance on the determination of the dose level for the next cohort. The dose recommendation relies on maximizing the probability of targeted toxicity while controlling the probability of excessive or unacceptable toxicity. This method will be applied to the observed data on an ongoing basis throughout the dose escalation. The toxicity-band method will stop early if the prespecified maximum number of patients is reached or the recommended next dose level has been administered to at least 6 patients.

During the dose-escalation period, the investigators and Lilly CRP or designee in consultation with collaborator will consider the model recommendation, the observed DLT rate, and any

DLT-equivalent toxicities observed in Cycle 2 and beyond at each cohort to determine the next dose level and determine when to stop dose escalation. Safety data, in particular, DLTs, will be the primary criteria for dose escalation. In addition, if available at the time of the dose-escalation decision, PK results will be used as secondary/supporting data for dose escalation. Additional patients may, therefore, be enrolled at a specific dose level to characterize PK/pharmacodynamics. No dose escalation can occur without prior discussion and agreement between the investigator and the Lilly CRP or designee in consultation with collaborator; the decision will be documented in writing.

The dose levels for dose escalation are provided in [Figure CXAD.6.1](#). The starting dose level will be 20 mg. The 20-mg and 30-mg dose levels will enroll 3 patients initially. The 40-mg dose level will enroll and treat 1 patient initially. After a 2-week observation period, the additional patients will be enrolled after notification from the sponsor. For all dose levels after the initial 3 patients have been enrolled, additional patients (at that dose level) may be enrolled in case of DLT. If deemed necessary, additional dose levels may be explored after discussion between the investigator and the Lilly CRP or designee in consultation with collaborator. The toxicity-band method has the ability to accommodate additional dose levels naturally. The DLT observation period will last for 4 weeks or to the completion of Cycle 1. Additional patients will be enrolled in a cohort to achieve the minimum of 3 evaluable patients if dropouts or dose interruptions occur that result in a patient being nonevaluable for DLTs due to nonmedical reasons. Patients who withdraw from the study during the DLT observation period for reasons other than a DLT may be replaced within the same dose level. For the purpose of making decisions on dose escalation from a safety perspective, patients will be considered evaluable (DLT-evaluable population) if they have either completed the DLT-observation period (Cycle 1) and received the scheduled durvalumab dose and at least 75% of LY2510924 doses in Cycle 1 or have discontinued study treatment or study participation before completing Cycle 1 due to a DLT. If the DLT-observation period is extended to Cycle 2, patients who discontinued during Cycle 2 in the absence of DLT-equivalent toxicity will be considered evaluable for DLT assessment.

Details regarding the toxicity-band method for this study are provided in [Attachment 9](#).

